7.2. Definition of Baseline Values

The baseline value is defined as the value collected at the time closest to, but prior to the start of study drug administration (BBI608 or TMZ, whichever was administered first). Values will be considered baseline if they are up to 10 days prior to first dose. An MRI scan performed within 28 days of the first schedule dose of BBI608 can be used for baseline assessment if it was performed while the patient was off steroids or on a stable or decreasing steroid dosage for at least 5 days; otherwise, MRI should be performed within 14 days of dosing. This will be the baseline scan for patients in Arm B; repeat MRI obtained within 48-72 hours following surgery will be the baseline scan for the patients in Arm A for purposes of response assessment.

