In the phase Ib/DLT cohort portion of this study, for both Arms A and B, pharmacokinetics will be evaluated on Day 1 and Day 5 of combination therapy with BBI608 and TMZ. Pharmacodynamics will be evaluated in all patients who undergo surgical resection.

For patients in Arm A during the run- in period with BBI608 monotherapy, the same DLT rules as for the combination therapy will apply. Enrollment will be held if ≥ 2 patients are unable to undergo resection due to DLTs. Enrollment will also be held if ≥ 2 patients have an unexpected surgical complication.

Initial enrollment will be to a 6-patient safety cohort in each arm. These patients will be evaluated for the occurrence of DLT during the first 28 days of combination treatment with BBI608 and TMZ. If DLT is observed in ≥ 2 of 6 patients evaluable for DLT, the initial dose of BBI608 for all patients in that arm will be reduced to the next lower dose level of 240mg twice daily and an additional 6-patient safety cohort will be enrolled at that dose-level and evaluated for DLT as above. Enrollment will continue at a dose-level at which ≤ 1 of 6 patients experiences DLT. Dose modification is allowed according to the standard schedule for BBI608.

It is expected that up to 30 patients (including those enrolled to the DLT evaluation cohorts) will be enrolled in each arm.

For all patients on study, tumor assessments will be performed at eight-week intervals or as clinically indicated. Disease status will be assessed by contrast-enhanced magnetic resonance imaging (MRI) of the brain.

Progression Free Survival will be assessed from the date of enrollment until objective disease progression or death. Tumor response and progression will be evaluated using RANO criteria. Patients who are enrolled in Arm A but who do not undergo surgical resection will be considered evaluable for tumor response utilizing the same assessment criteria as employed for patients in Arm B. All patients will be followed for disease progression and included in time-to-event analyses.

Patients will continue treatment with BBI608 and TMZ until the investigator has determined that they are no longer clinically benefiting due to progression of

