3.1 Inclusion Criteria

Each patient must meet the following criteria to be enrolled in this study.

1. Signed written informed consent must be obtained and documented according to International Conference on Harmonisation (ICH) and local regulatory requirements
2. A histologically confirmed supratentorial GBM at first recurrence/progression following standard front-line therapy, for which treatment with TMZ would be acceptable as determined by the Investigator.
 - a. Recurrence is defined as progression following initial therapy (i.e. radiation+/- chemo, if that was used as initial therapy). The intent therefore is that the patient has had no more than 1 prior treatment regimen.
3. Previously received standard front-line GBM treatment including maximal surgical resection followed by external beam radiation therapy.
 - a. Prior concurrent chemoradiation with TMZ is allowed but not mandatory. A minimum of 12 weeks following the last dose of Radiotherapy or TMZ-Radiotherapy must occur prior to the first documented progression. After that period in patients receiving adjuvant TMZ a wash out period of 4 weeks before first dose of BBI608 is required.
4. Patients may or may not be candidates for repeat surgical resection of the recurrent/progressed GBM.
5. Patients must have unequivocal evidence of tumor recurrence/progression by MRI at a minimum of 12 weeks following completion of chemoradiation or radiation therapy.
6. Baseline scan performed within 28 days of enrollment.
7. Patients on concurrent corticosteroid treatment are eligible for enrollment as long as they are on a stable or decreasing dose of corticosteroids (or no corticosteroids) and neurologically stable from the time of their baseline scan and/or at least 5 days before starting treatment with BBI608. During this period the maximum total daily dose of dexamethasone should not exceed 8 mg administered orally (or bioequivalent).

8. Patients must have measurable or non-measurable disease by RANO criteria.
9. Patients treated with CYP1A2 enzyme inducing anti-epileptics (including phenobarbital, phenytoin, and carbamazepine) must be switched to an alternative anti-epileptic agent at least 14 days prior to first dose of BBI608.
10. ≥ 18 years of age.
11. ECOG (Eastern Oncology Cooperative Group) performance status of 0 or 1 (corresponding to a Karnofsky performance status score $\geq 70\%$) (Appendix C).

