5.4.2 Surgical Resection of Recurrent GBM

ONLY patients enrolled into Arm A will undergo surgical resection of GBM.

BBI608 will be administered for 7 (\pm 2) days prior to a planned surgical resection of recurrent GBM. BBI608 will be administered on the morning of the surgical procedure (Run-in Week 2 Day 8) and BBI608 will remain held pending clinical post-operative recovery of the patient as determined by the investigator, for up to 28 days after surgery. Tumor sample will be obtained at time of surgical resection from T1/gadolinium enhanced lesion(s) as well as T2/FLAIR infiltrating tumor lesions and will be used to investigate BBI608 presence in the resected tumor tissue and will be used for pharmacodynamics analysis (please see the Laboratory Manual for additional information). Additionally, blood sample will be obtained at time of surgery to evaluate BBI608 pharmacokinetic (PK) exposure in the plasma (please see the Laboratory Manual for additional information). The time of BBI608 administration on the day of surgery and the collection times of blood sample will be recorded.

Tumor samples that are obtained at the time of surgical resection and are labeled with study protocol identification number and patient identification number will be sent to a regulatory authority-approved tumor bank affiliated with the study site, or to the study site pathology department if the site does not have a regulatory authority-approved tumor bank. In the event

that there is difficulty with establishment of histological diagnosis, tumor tissue will be made available to the pathology department at all study sites. Processing of all tumor tissue will include creation of both fresh frozen samples for PK analysis as well as blocks of formalin fixed paraffin-embedded (FFPE) samples for PD analysis.

An MRI will be performed 48-72 hours following surgery and will be used as the baseline scan for the purposes of tumor response evaluation in the patients who undergo surgical resection.

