10.2. Appendix 1.2 Censoring for Time to Event Data

Table 4 summarizes the censoring rules for the PFS analysis and displays censoring hierarchy for this study. Table 5 shows the general reasons for PFS censoring and where the censoring hierarchy in **Table 4** came from.

Table 4 Event or Censor Time for PFS and Censoring Hierarchy

Censoring Hierarchy	Situation	Date of Event or Censor	Event / Censor
1	No baseline radiological tumor assessment available	Date of First Dose	Censored
2	New anticancer treatment started and no tumor progression	Date of previous adequate radiological assessment immediately prior to start of new therapy or Date of first dose, whichever comes later	Censored
3	Tumor progression (per RANO) documented after 2 scan intervals following previous adequate radiological tumor assessment	Date of previous adequate radiological assessment or Date of first dose, whichever comes later	Censored
4, 5	No tumor progression (per RANO) and subject lost to follow-up or withdrawal of consent	Date of last adequate radiological Assessment or Date of first dose, whichever comes later	Censored
6	No post baseline radiological tumor assessment available and no death reported within 2 scan intervals following the date of the first dose of study drug (BBI608)	Date of First Dose	Censored
7	No post baseline radiological tumor assessment available but death reported within 2 scan intervals following the date of the first dose of study drug (BBI608)	Date of Death	Event

	No tumor progression (per RANO) and no death reported within 2 scan intervals following last adequate radiological tumor assessment	Date of last adequate radiological tumor assessment or Date of first dose, whichever comes later	Censored
	No tumor progression (per RANO) but death reported within 2 scan intervals following last adequate radiological tumor assessment	Date of death	Event
	Tumor progression (per RANO) documented within 2 scan intervals following previous adequate radiological tumor assessment	Earliest of the target, non-target and new tumor assessment dates	Event

Notes: (1) Symptomatic deteriorations (i.e. symptomatic progressions, which are not radiographically confirmed) will not be considered as progressions.

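### SAP 7.2 and Table 4 can be read together to censor at Day 1 any Arm A patient without a post-operative MRI, even one who dies or progresses

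*SAP*

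**What the plan says.** SAP 7.2 starts from a general rule: baseline is "the value collected at the time closest to, but prior to the start of study drug administration". For imaging it adds that "An MRI scan performed within 28 days of the first schedule dose of BBI608 can be used for baseline assessment", subject to a steroid condition. It then assigns scans by arm. The pre-treatment MRI is the baseline for Arm B, while for the other arm "repeat MRI obtained within 48-72 hours following surgery will be the baseline scan for the patients in Arm A for purposes of response assessment". Protocol 5.3 has almost the same wording.

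Elsewhere the protocol is narrower. Under section 5.4.2 the post-operative MRI "will be used as the baseline scan for the purposes of tumor response evaluation in the patients who undergo surgical resection", and sections 5.5 and 9.3 carry the same limit. For the remaining Arm A patients the synopsis (Study Design) states: "Patients who are enrolled in Arm A but who do not undergo surgical resection will be considered evaluable for tumor response", using the Arm B criteria. It goes on: "All patients will be followed for disease progression and included in time-to-event analyses".

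For PFS, Table 4 in SAP Appendix 1.2 gives first rank to this situation: "No baseline radiological tumor assessment available". Such a patient is censored at the date of first dose. The row has no exception for a later death or progression. The rows that count an early death or a timely progression as an event come below it. Table 5 also ranks a missing adequate baseline first.

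**The concern.** The SAP drops the protocol's limit to resected patients and does not carry over the Arm B fallback for the rest. Three kinds of Arm A patient can lack a post-operative MRI: those never resected, those who die around surgery, and those whose scan is missed. If the post-operative MRI is their only recognised baseline, row 1 applies and their follow-up is discarded from Day 1.

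Death from any cause is a PFS event in SAP 8.2.3.1 and Appendix 1.1, and recognising it needs no baseline scan. Patients whose surgery is cancelled for toxicity or progression, or who die peri-operatively, may well fail early, so the censoring could be informative. It would affect the primary endpoint, PFS-6, and median PFS in Arm A, and would run against the synopsis statement that all patients enter the time-to-event analyses.

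The protocol foresees such patients: it provides for unresected Arm A patients in the synopsis, and it holds enrollment if two or more cannot have resection because of DLTs. Under the same reading, SAP 7.1 would count them as non-responders for ORR and DCR while PFS drops them.

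**Working it through.** **The plan's own figure.** Protocol 10.2 and SAP 4.2.2 take n = 30 per arm, a projected PFS-6 of 20% (6 of 30) and a two-sided 80% exact binomial interval, and state a lower bound above 10%. The Clopper-Pearson lower limit is the 0.10 quantile of Beta(6, 25), which is 10.9%. The figure is reproduced.

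**What row 1 does when it applies.** SAP 8.2.2.2 computes PFS as (event or censoring date − first dose date + 1)/30.4375. Censoring at first dose gives 1/30.4375 = 0.033 months. The patient leaves every later Kaplan-Meier risk set.

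**Does row 1 apply?**
- *Unresected patient.* SAP 7.2 names a scan that cannot exist. The protocol gives a fallback (assess as in Arm B, so against the pre-study MRI), but the SAP does not repeat it.
- *Resected patient without the scan.* Neither document gives a fallback.
- *In both cases* a pre-study MRI is required by Protocol 3.1 ("Baseline scan performed within 28 days of enrollment"). The SAP never says whether it makes a baseline available for row 1. If it does, row 1 is not met, and a death within 2 scan intervals of first dose with no post-baseline scan is an event. If it does not, the patient is censored at Day 1. Two programmers could each follow the SAP and differ.

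**Size under the Day 1 reading.** Assume 30 Arm A patients, 6 event-free at 6 months, no other censoring, and k patients without a post-operative MRI who all fail before month 6. The documents give no value for k.

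Point estimate: S = 6/(30 − k).

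Interval planned in SAP 8.2.2.2 (log cumulative hazard scale, 80%): with n = 30 − k, se = √[(1 − S)/(nS)]/|ln S|, and the limits are S raised to the power exp(±1.28 × se). For k = 0: √(0.8/6) = 0.365; 0.365/1.609 = 0.227; exp(1.28 × 0.227) = 1.34; 0.2^1.34 = 11.6%.

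| k | PFS-6 | 80% interval |
|---|---|---|
| 0 | 6/30 = 20.0% | 11.6 to 30.0% |
| 2 | 6/28 = 21.4% | 12.5 to 32.0% |
| 3 | 6/27 = 22.2% | 12.9 to 33.1% |
| 5 | 6/25 = 24.0% | 14.0 to 35.5% |

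If the pre-study MRI counts and the events are kept, the result is the first line whatever k is.

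**Dependence on early failure.** If 1 of 5 affected patients were event-free at 6 months, censoring all 5 would give 5/25 = 20.0%, with no shift. The bias exists only if these patients do worse than the rest.

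**The case against.** A reader might infer that the SAP declares these patients to have no baseline and orders their censoring at Day 1. The documents do not support that. Row 1 depends on whether a baseline assessment is available, and the pre-study MRI is required of every patient; Appendix A schedules it for Arm A. SAP 7.2 gives the post-operative scan its role only for response assessment, calls it a repeat MRI, and in the same paragraph accepts a pre-dose MRI for baseline. Note 4 to Table 4 envisages a baseline scan that may precede first dose, whereas the Arm A post-operative scan always follows it. The SAP sentence also nearly copies Protocol 5.3, so it looks like inherited shorthand rather than a new rule.

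All of this stands, and it makes Day 1 censoring one reading rather than the rule. It does not settle the matter. Progressive disease is itself a RANO response category, so the phrase about response assessment does not clearly leave PFS out. Protocol 5.3 conflicts with 5.4.2, 5.5 and 9.3. Resected patients without the scan have no provision anywhere.

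The size can also be over-read. A refused operation or a missed scan is not in itself evidence of early failure, and the shifts lie well inside the 80% interval. With 5 of 30 event-free, the planned lower bound moves from 9.1% to 10.1% at k = 3, but this is not a changed decision: SAP 4.1 has no hypothesis test, and the 10% describes precision rather than a go/no-go limit.

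**Conclusion.** The concern holds as an ambiguity in the primary endpoint. SAP 7.2 is broader than the protocol sections that limit the post-operative baseline to resected patients, and with Table 4, row 1, it permits Day 1 censoring of Arm A patients who die or progress. The direction is upward for PFS-6 and median PFS if those patients tend to fail early. In the illustration the shift in PFS-6 is 1.4, 2.2 or 4.0 percentage points for k = 2, 3 or 5, and the planned 80% lower bound moves from 11.6% to 12.5%, 12.9% or 14.0%.

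This rests on an assumed k, on every affected patient failing before month 6, on no other censoring, and on the SAP's full analysis set. The protocol's per-protocol population, which requires most of a combination cycle, would already leave out peri-operative deaths. The point deserves correction before the analysis is programmed, but it ranks below a must-fix.

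**What to change.** 1. **SAP 7.2.** Limit the post-operative baseline to Arm A patients who undergo resection. For unresected Arm A patients, name the pre-study MRI as baseline, as in Arm B.
2. **Table 4, row 1.** Treat the pre-study MRI as an available baseline, so that the row applies only when there is no scan of either kind. State that a death within 2 scan intervals of first dose is a PFS event whether or not a baseline scan exists. Align Table 5.
3. **Resected patients without a post-operative MRI.** Counting the pre-study MRI for row 1 keeps them in the PFS risk set, but it should not become their measurement baseline. Against a pre-operative scan, debulking could be scored as a response of 50% or more, and regrowth could go unnoticed. Keep them as non-responders for ORR. For PFS, count death and any RANO progression that does not depend on the missing scan, such as a new lesion. Say also that their on-study scans count as adequate when dating a censoring, since note 3 to Table 4 otherwise requires an overall response of CR, PR, SD or PD.

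The cost is wording in the SAP and a matching change to Protocol 5.3. No new data are needed, because the pre-study MRI is already required in both arms. Arm A PFS-6 may come out slightly lower.

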7.3. Visit Windows

All data will be categorized based on the scheduled visit at which it was collected. These visit designators are predefined values that appear as part of the visit tab in the eCRF.

7.4. Dropouts

Time to event parameters will be censored if patients drop out (withdraw from consent or lost to follow-up) before documentation of the events (progressive disease / death). Rules for censoring for PFS are detailed in 10.2

7.5. Pharmacokinetics

For individual concentration-time plots and the calculation of PK parameters using noncompartmental analysis, individual BLQ values will be converted using the following rules:

- If a BLQ value occurs in a profile before the first quantifiable concentration, it will be assigned a value of zero.
- If a BLQ value occurs after a quantifiable concentration in a profile and is immediately followed by a value above the LLQ, then the BLQ value should be treated as missing.
- If a BLQ value occurs at the end of the collection interval (after the last quantifiable concentration) it will be treated as missing.
- If two BLQ values occur in succession after C_{max}, the profile will be deemed to have terminated at the first BLQ value and any subsequent quantifiable concentrations will be omitted from PK calculations by treating them as missing.

When imputing BLQ concentrations for the generation of summary statistics at a given time point, all BLQ values will be set to zero except when an individual BLQ falls between two quantifiable values, in which case it will be treated as missing. These same imputations apply to imputation of BLQ concentrations used for generation of concentration-time profiles based on summary statistics.

7.6. Pharmacodynamic parameters

Missing data for the pharmacodynamic parameters will be treated as such and no imputed values will be derived.

8. STATISTICAL METHODOLOGY AND STATISTICAL ANALYSES

8.1. Statistical Methods

Whilst every effort has been made to pre-specify all analyses in this statistical analysis plan, if any additional exploratory analyses be found to be necessary, the analyses and the reasons for them will be detailed in the clinical study report (CSR).

8.1.1. Analysis for Time to Event Data

Time-to-event endpoints will be summarized using the Kaplan-Meier method and displayed graphically when appropriate. Median event times and 2-sided 95% confidence intervals for each time-to-event endpoint (2) will be provided. There will be no subjects that remain in follow-up because sponsor has terminated all follow-up after 29JUN2018.

8.1.2. Analysis for Binary Data

Point estimates of binary endpoints for each treatment arm will be provided along with the corresponding 2-sided 95% confidence intervals using an exact method (3).

8.1.3. Analysis for Continuous Data

Descriptive statistics, such as the mean, standard deviation, median, minimum, and maximum values, will be provided for continuous endpoints. Linear or non-linear models may be employed to analyze the continuous data.

8.2. Statistical Analyses

8.2.1. Standard Analysis

Standard analysis below will be conducted by arm. Overall summary for each arm will also be provided. Adverse Events, Concomitant Medications, and Medical History will be coded.

Study Conduct and Patient Disposition

Patient disposition includes the number and percentage of patients for the following categories: patients in each of the study populations, patients discontinued from the treatment, primary reason to discontinue from the treatment, and patients discontinued from the study. All percentages will be based on the number of patients in the full analysis dataset (FAS).

Demographic and Baseline Characteristics

Baseline characteristics such as demographics, baseline disease characteristics, prior therapies, and ECOG performance status score will be tabulated and listed.

Prior and concomitant medications

Prior and concomitant medications will be coded to ATC (Anatomical Therapeutic Chemical) classification and Drug Name using WHO Drug Dictionary (WHO-DD) version 19.0 March 2016.

Summaries of concomitant medications will be provided by level 3 ATC classification and preferred term using frequencies and percentages for the full analysis set.

Prior Treatment

Prior treatment will be summarized by arm and listed for each patient in the full analysis set.

Prior cancer surgery will be summarized by type and procedure. The number and percentage of subjects in each type of prior cancer surgery will also be reported by overall.

The total dose and type of prior cancer radiotherapy will be summarized. The number and percentage of subjects with the various anatomical locations will be reported.

The type, treatment setting, and number of prior cancer Hormone/Biologics/Chemotherapy/Other will be summarized. The number and percentage of patients reporting each category will be reported.

Medical History

Medical history will be coded by SOC and PT using MedDRA. Medical history will be summarized by SOC and PT using the number and percentage of patients for the full analysis set.

Duration of Follow-up

The duration of follow-up is defined as time from the date of first dose of study treatment to the death or last known visit. If a subject dies, the duration is equal to date of death minus study start + 1 with censor variable =1 (censored for follow up). If a subject is alive, the duration is equal to the date subject last known to be alive minus study start + 1 with censor variable=0 (event for follow up).

Extent of Exposure

Exposure may be summarized (overall and by period for Arm A subjects) as dose received (cumulative dose or actual dose intensity) or as dose received relative to intended dose (relative dose [RD], or relative dose intensity [RDI]), or both.

The information that will be summarized depends on how the study drug is dosed (e.g., infusion cyclical, oral daily, oral cyclical).

In what follows “time unit” can be e.g., weeks or days.

Drug accountability will be summarized in a listing.

Intended treatment duration = intended end of treatment date – date of first dose of study drug +1, where the intended end of treatment date is (start date of last cycle + intended cycle duration – 1 day) for each treatment arm

- For BBI608, intended cycle duration= $\max\{28, \text{date of last dose of the cycle} - \text{date of first dose of the cycle} + 1\}$
- For BBI608 in pre-surgical period for Arm A patients, intended cycle duration= surgical procedure date – first dose date + 0.5. Subjects in Arm A took BBI608 in the morning of the surgical procedure and thus took a half day’s dose of BBI608.
- For cyclic combination drug TMZ, intended cycle duration=5 days

Actual treatment duration = actual end of treatment date – date of first dose of study drug +1,

- For BBI608 and TMZ, actual end of treatment date is last dosing date

Cumulative dose in a period (for Arm A subjects), cycle, or overall for BBI608 is the sum of the actual doses received in a period or cycle or overall, respectively. Cumulative dose overall for TMZ is the sum of the actual doses received overall.

Actual Dose Intensity [DI]

- For Arm A subjects: By period actual DI (*dose unit/week*) = [cumulative dose in the period]/[intended period duration in weeks]
- By cycle actual DI (*dose unit/week*) = [cumulative dose in cycle] / [intended cycle duration in *weeks*].
- Overall actual DI (*dose unit/week*) = [overall cumulative dose] / [intended treatment duration in *weeks*].

Relative dose [RD]: The basic intent is to evaluate dose per *week* factoring in dose reductions or interruptions.

- Relative dose by period (Arm A subjects), by cycle and overall
 - By period RD (%) = $100 \times [\text{cumulative dose in the period}] / [\text{intended cumulative dose per period}]$
 - By cycle RD (%) = $100 \times [\text{cumulative dose in the cycle}] / [\text{intended cumulative dose per cycle}]$
 - Overall RD (%) = $100 \times [\text{overall cumulative dose}] / [\text{total planned or intended dose}]$
- For a combination regimen
 - if a study drug is discontinued prematurely while other study drug(s) are continued, then the RD is 0 for the discontinued study drug until all other study drug(s) of the regimen are discontinued

Relative Dose Intensity (RDI): The basic intent is to evaluate dose per *week* factoring in dose reductions, interruptions, or delays.

- Relative dose intensity (RDI) by period (Arm A subjects), by cycle and overall
 - Intended DI (*dose unit/week*) = [intended cumulative dose per period/cycle] / [intended number of *weeks* in a period/cycle]
 - By period RDI (%) = $100 \times [\text{by period actual DI}] / [\text{intended DI}]$
 - By cycle RDI (%) = $100 \times [\text{by cycle actual DI}] / [\text{intended DI}]$
 - Overall RDI (%) = $100 \times [\text{overall actual DI}] / [\text{intended DI}]$

Note:

- The intended dose level is fixed at the start of treatment rather than the start of a cycle.

- The intended cumulative dose of BBI608 per period (for Arm A subjects) is calculated by (intended dose level per day) x (intended period duration in days).
- The intended cumulative dose of BBI608 per cycle is calculated by (intended dose level per day) x (intended cycle duration in days).
- Dose unit of BBI608 is mg; dose unit of TMZ is mg/m².

Treatment compliance

BBI-608 compliance will be summarized by period (for Arm A), for cycle 1 (Arm A post-operative and Arm B patients) and overall

1. By Period (Arm A): Treatment compliance for BBI-608 is defined as below, (Cumulative actual total dose per period/ total planned or intended dose per period) x 100=% compliance
2. By Cycle (Arm A post-operative and Arm B): Treatment compliance for BBI608 is defined as below, (Cumulative actual total dose per cycle /total planned or intended dose per cycle) x 100= % compliance
3. Overall: Treatment compliance for BBI-608 is defined as below, (Cumulative actual total dose /total planned or intended dose) x 100= % compliance
4. Daily treatment compliance will be reported for each patient for the following dose-levels and intervals
 - The % of days the patient received a total dose of at least 960 mg BBI608 out of intended treatment duration in days.
 - The % of days the patient received a total dose of at least 480 mg BBI608 out of intended treatment duration in days.
 - The % of days the patient received a non-zero dose of BBI608 out of intended treatment duration in days.

Daily treatment compliance will be grouped according to the following categories: < 60%, ≥ 60% - < 80%, ≥ 80% - < 90%, ≥ 90%, and will be summarized for the treatment group of BBI608 Plus TMZ and BBI608 (for pre-surgery period for Arm A).

Combination drug compliance overall

5. Overall: For TMZ, compliance will be calculated using the following equation: (Number of treatments administered /number of treatments that should have been administered) x 100= % compliance

